#### **8.2.4.2 Safety Analysis Populations**

The All-Subjects-as-Treated (ASaT) population will be used for the analysis of safety data in this study. Randomized subjects with invasive aspergillosis and chronic pulmonary aspergillosis (chronic progressive pulmonary aspergillosis and simple pulmonary aspergilloma) will be pooled for the analyses but subjects with fusariosis and zygomycosis, not randomized subjects, will be separately evaluated. The ASaT population consists of all randomized subjects in cohort 2 who received at least one dose of study treatment. Subjects will be included in the treatment group corresponding to the study treatment they actually received for the analysis of safety data using the ASaT population.

At least one laboratory or vital sign measurement obtained subsequent to at least one dose of study treatment is required for inclusion in the analysis of each specific parameter. To assess change from baseline, a baseline measurement is also required.

#### **8.2.5 Statistical Methods**

The main objective of this study is assessment of safety and the formal hypothesis testing for efficacy endpoints will not be conducted. Nominal p-values and confidence intervals will be presented at the  $\alpha=0.05$  (2-sided) level.

##### **8.2.5.1 Statistical Methods for Efficacy**

###### **8.2.5.1.1 Primary Efficacy Analysis**

The primary efficacy endpoint is the overall response assessed by CAC. The overall response rates (the proportion of subjects with “success” assessment) for invasive aspergillosis at Day 42 and for chronic pulmonary aspergillosis (chronic progressive pulmonary aspergillosis and simple pulmonary aspergilloma) at Day 84 and their 95% confidence intervals will be computed by treatment. Subjects with solid oral tablet, IV solution and switch from IV solution to solid oral tablet for the MK-5592 treatment arm will be pooled for the analyses due to the fact that it reflects clinical practice and the different routes of administration achieve targeted plasma concentration level of MK-5592. Likewise, subjects with oral tablet, IV solution and switch from IV solution to oral tablet for the Voriconazole treatment arm will be pooled for the analyses. The 95% confidence intervals will be estimated with the Clopper-Pearson method.

### 8.2.5.1.2 Secondary Efficacy Analysis

The overall response rates for invasive aspergillosis at Day 84 and for chronic pulmonary aspergillosis (chronic progressive pulmonary aspergillosis and simple pulmonary aspergilloma) at Day 42 will be provided by treatment ([Table 26](#)).

The overall response rate for all aspergillosis (invasive aspergillosis and chronic pulmonary aspergillosis are pooled) at EOT will be provided by treatment.

Clinical, radiological and mycological response rates for invasive aspergillosis and for chronic pulmonary aspergillosis (chronic progressive pulmonary aspergillosis and simple pulmonary aspergilloma) at Day 42 and Day 84 will be provided by treatment.

The overall response for the subjects with fusariosis and zygomycosis will be listed for MK-5592 treatment arm since the enrollment of these infections will be very limited.

As a sensitivity analysis, the overall response rates for invasive aspergillosis at Day 42 and for chronic pulmonary aspergillosis at Day 84 will be provided by treatment in the PP population. For the PP analysis, a subject with missing post-treatment response data or with 'unable to determine' response will be excluded. In addition, the overall response rates will be provided in the ITT population and also the overall response rates by investigators/sub-investigators will be provided in the FAS population.

Table 26 Analysis Strategy for Key Efficacy Variables

Endpoint/Variable (Description, Time Point)	Primary vs. Supportive Approach	Statistical Methods	Analysis Population	Missing Data Approach
Primary				
Overall response rates for invasive aspergillosis at Day 42 and for chronic pulmonary aspergillosis at Day 84	P	95% CI with Clopper-Pearson Exact Method	FAS	CF †
	S	Point Estimate	PP	CF †
	S	Point Estimate	ITT	CF †
	S	Point Estimate: Assessment by investigators/sub-investigators	FAS	CF †
Secondary				
Overall response rates for invasive aspergillosis at Day 84 and for chronic pulmonary aspergillosis at Day 42	P	Point Estimate	FAS	CF †
Overall response rate for all aspergillosis at EOT (invasive aspergillosis and chronic pulmonary aspergillosis are pooled)	P	Point Estimate	FAS	CF †
Clinical response rates, radiological response rates and mycological response rates for invasive aspergillosis and for chronic pulmonary aspergillosis at Day 42 and Day 84	P	Point Estimate	FAS	CF †

†CF: Carried-forward method

#### 8.2.5.1.3 [REDACTED]

[REDACTED]

[REDACTED]

#### 8.2.5.1.4 Accounting for Missing Data

For the primary analyses in FAS and ITT (overall response rates for invasive aspergillosis at Day 42 and for chronic pulmonary aspergillosis at Day 84), missing data will be imputed by a carried-forward method. Baseline values will not be carried forward and if there is no data after treatment, the missing data will be considered as failure. Data with ‘unable to determine’ will be considered as failure as well. For the overall response rates for invasive aspergillosis at Day 84 and for chronic pulmonary aspergillosis at Day 42, and also clinical, radiological and mycological response rates at Day 42 and Day 84 for both aspergillosis, the missing data will be imputed likewise.

For the analyses in PP population, a subject with missing post-treatment response data or with ‘unable to determine’ response will be excluded.

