#### **4.2.3 Rationale for Endpoints**

Safety and efficacy endpoints in this study are based on the EORTC/MSG criteria [14, 15], endpoints of MK-5592 clinical study conducted outside Japan, endpoints of clinical study for chronic pulmonary aspergillosis conducted in and outside Japan [16, 17], and the guideline as antifungal drugs evaluation committee by Japan chemotherapy association March 2012 [18]. Deep-seated fungal infection is usually manifested in immunocompromised subjects with serious underlying diseases (such as HIV, organ transplantation, and cancer). For such infections, the assessment of efficacy usually takes into consideration a number of key variables, including the response to clinical signs and symptoms (Clinical Response), the response to mycological measures of the infection (Mycological Response), and the response to radiological evidence of the infection (Radiological Response). Therefore, an overall response, which encompasses many of these individual components, is routinely applied to the assessment of efficacy in these types of infections. Overall response criteria for invasive aspergillosis is set in 5 levels (complete response, partial response, stable response, progressive disease and unable to determine). Success is defined as complete response and partial response. Failure is defined as stable response, progressive disease and unable to determine. Overall response criteria for chronic pulmonary aspergillosis is set in 4 levels (favorable response, stable response, progressive disease and unable to determine). Success is defined as favorable response. Failure is defined as stable response, progressive disease and unable to determine. For chronic pulmonary aspergillosis, it is rare that ‘finding of imaging’ are resolved. Complete response and partial response are not set but favorable response is set in overall response. The overall response is evaluated by the investigator or sub-investigator according to the criteria. The overall response is finally evaluated by the clinical adjudication committee.

For subject with IA, we set the endpoint at Day 42 same as global study (069 study) in order to be able to confirm the efficacy between 101 and 069 study. For subject with CPA, we set the endpoint at Day 84 same as registration clinical studies conducted with using other anti-fungal drugs in the subject with CPA in Japan.

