**Criteria for Overall Response**

Table 10 Overall Response Criteria for Invasive Aspergillosis, Zygomycosis and Fusariosis

		Clinical Response				
		Resolution	Improvement	Stabilization	Worsening	Unable to determine
Radiological Response	Resolution	Complete Response	Partial Response	Partial Response	Progressive Disease	Unable to determine
	Improvement	Partial Response	Partial Response	Partial Response	Progressive Disease	Unable to determine
	Stabilization	Partial Response	Partial Response † / Stable response †	Stable Response	Progressive Disease	Unable to determine
	Worsening	Progressive Disease	Progressive Disease	Progressive Disease	Progressive Disease	Progressive Disease
	Unable to determine	Unable to determine	Unable to determine	Unable to determine	Progressive Disease	Unable to determine

†: Assessment based on the Mycological Response in below

- In case of “Detected at Screening” and “Undetected at the Evaluation”, Mycological Response and Overall Response are “Resolution” and “Partial Response”, respectively.
- In case of “Undetected at Screening” and “Undetected at the Evaluation”, Mycological Response and Overall Response are “Stabilization” and “Stable Response”, respectively.
- In case of “Detected at Screening” and “Detected at the Evaluation”, Mycological Response and Overall Response are “Stabilization” and “Stable Response”, respectively.
- In case of “Undetected at Screening” and “Detected at the Evaluation”, Mycological Response and Overall Response are “Worsening” and “Stable Response”, respectively.

Table 11 Overall Response Criteria for Chronic Pulmonary Aspergillosis

		Clinical Response			
		Improvement	Stabilization	Worsening	Unable to determine
Radiological Response	Improvement	Favorable Response	Favorable Response	Progressive Disease	Unable to determine
	Stabilization	Favorable Response	Stable Response	Progressive Disease	Unable to determine
	Worsening	Progressive Disease	Progressive Disease	Progressive Disease	Progressive Disease
	Unable to determine	Unable to determine	Unable to determine	Progressive Disease	Unable to determine

Table 12 Overall Response Criteria for in Case of Zygomycosis and Fusariosis Without Imaging

		Clinical Response				
		Resolution	Improvement	Stabilization	Worsening	Unable to determine
Mycological Response	Eradication	Complete Response	Partial Response	Stable Response	Progressive Disease	Unable to determine

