Scheduling Window Days	-	-	+2	+/-1	+/-3	-3 to +7	+/-6	+2	-1	+7	-
Dispensing and collecting of study drug, confirmation for number of study drug		x								x	x
Issuing, collecting and confirming the medication diary (oral administration)		x								x	x
Assessment of overall response (including clinical response, radiological response, and mycological response) 					xx	x	xx	x	x		
Adverse Events Monitoring		← Continuing to confirm →									x

x: must be done

xx: will be done as needed

1. Procedure must be done before the initiation of study therapy. If conducted on a same date, measurement and evaluation is not needed 2 times.
2. 12-lead ECG is tried to perform at the timing of maximum serum drug concentration. Recommended timing is as follows;
  - MK-5592 IV solution: just after the end of treatment
  - MK-5592 solid oral tablet: 3 to 5 hours after the treatment
  - Voriconazole IV: just after the end of treatment
  - Voriconazole oral tablet: 1 to 2 hours after the treatment
3. Subjects enrolled with a part of these testings, mycology testing and mycological serology testing (aspergillus antigen, antibody and β-D-glucan) must be performed. Mycological testings must be performed during the treatment and EOT excluding eradication of the sample enable to collect. Aspergillus antibody is performed for the subject with chronic pulmonary aspergillosis and is performed at the screening only. Serology testing is no need for subjects with Zygomycosis and Fusariosis
4. Data comes from within 7 days before initiation of study therapy, it can be used as a screening result. For the mycology test (culture testing, direct microscopy or histopathological examination etc.), data comes from within 14 days before initiation of study therapy can be used as a screening result. Aspergillus antibody testing, data comes from within 28 days before initiation of study therapy can be used as a screening result. Mycology test shroud be done by following 7.1.2.6 Mycology Testing and the isolated fungus should be provided to the central laboratory.
5. Only for the subject with invasive aspergillosis.
6. Intravenous treatment (The plasma samples for PK evaluation in the subjects with zygomycosis during the extension period will not be needed)

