#### **7.1.2.9 Evaluation for Overall Response**

The individual response assessment (Clinical Response, Radiological Response, Mycological Response and Clinical Laboratory Response) in subjects with deep-seated fungal infection will be evaluated at Day 42, EOT(before the transition to the extension period) and switching formulation according to the criteria described in 4.2.3.1, and Overall Response is assessed based on these individual responses (However, if the subject is a patient with zygomycosis and joins the extension period, the individual response assessment at switching formulation or the last dose of MK-5592 therapy in the extension period does not need to be done). Overall response assessed by investigator and information are provided to the Clinical adjudication committee. CAC assessed the overall response according to the same criteria. The assessment by CAC is used as a Primary efficacy endpoint.

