### **7.1.4 Other Procedures**

#### **7.1.4.1 Withdrawal/Discontinuation**

When a subject discontinues/withdraws prior to trial completion, all applicable activities scheduled for the final trial visit should be performed at the time of discontinuation. Any adverse events which are present at the time of discontinuation/withdrawal should be followed in accordance with the safety requirements outlined in Section 7.2 - Assessing and Recording Adverse Events.

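### The carry-forward rule in Section 8.2.5.1.4 does not score death, so a patient dead by the target day can count as a responder in FAS and ITT

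*Combined protocol and SAP*

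**What the plan says.** The primary efficacy endpoint is the overall response rated by the Clinical Adjudication Committee (CAC), at Day 42 for invasive aspergillosis (IA) and at Day 84 for CPA (Section 8.2.3.1.1). For FAS and ITT, Section 8.2.5.1.4 sets the rule: "missing data will be imputed by a carried-forward method. Baseline values will not be carried forward and if there is no data after treatment". The exception for patients without post-baseline data reads in full: "if there is no data after treatment, the missing data will be considered as failure". It also scores a rating of unable to determine as failure. The same imputation applies to the secondary rates, introduced by "For the overall response rates for invasive aspergillosis at Day 84 and for chronic pulmonary aspergillosis at Day 42", and to the component responses.

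Section 4.2.3 gives the outcome definition: "Failure is defined as stable response, progressive disease and unable to determine". Table 25 repeats it. Death appears in neither place, nor in Tables 7 to 12, nor in the visible endpoint and analysis text of Section 8. For this trial's own data, death is mentioned only under serious adverse event reporting and adverse event grading (Section 7.2).

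On timing, Section 7.1.2.9 says the individual responses, from which the overall response is derived, "will be evaluated at Day 42, EOT(before the transition to the extension period) and switching formulation". The flow chart makes overall response as-needed at Days 56 and 70 and schedules no imaging there. For early stopping, Section 7.1.4.1 says "all applicable activities scheduled for the final trial visit should be performed at the time of discontinuation".

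**The concern.** The endpoint is response on a fixed day. A rule that carries the last rating forward and names only two failure cases lets a recorded success stand for a patient who is known to have died before that day. Such an error can only raise the reported rate, and it sits in the primary FAS analysis and in its ITT support, so neither exposes the other.

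The visible text also leaves open whether a response absent because of death is missing (carried forward, possibly a success) or unable to determine (a failure). Two analysts following the SAP could score the same patient in opposite ways.

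**Working it through.** **1. Routes by which a success can be carried past death**

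- *CPA, Day 84 (primary).* Favorable at the required Day 42 assessment, then death before Day 84 with no end-of-treatment (EOT) rating. Post-treatment data exist, so the failure clause does not apply and the Day 42 success is carried. A second route is early completion, for example for cure (Section 5.2.1.3), with a success at that EOT and death afterwards.
- *IA, Day 42 (primary).* Narrower. It needs an earlier success at a formulation switch, an as-needed visit or an early EOT.
- *IA, Day 84 (secondary).* A success at the required Day 42 assessment is enough.

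In CPA the carried rating bridges 84 − 42 = 42 days. With the Day 42 window of −3 to +7 (Days 39 to 49), that is 84 − 49 = 35 to 84 − 39 = 45 days.

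**2. The plan's own precision figures**

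Section 8.2.7 gives lower limits of 46.5% and 67.7% for response rates of 60% and 80% with 60 patients. Clopper-Pearson limits for 36/60 and 48/60 reproduce both. Neither depends on how death is scored.

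**3. Group sizes**

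From Section 8.2.7: 90 patients, 2:1, with a target of 15 IA. That leaves 90 − 15 = 75 CPA, split 50 and 25, and IA split 10 and 5. Assumption: all enter the FAS. For sensitivity, 80% is also assumed; the documents give no such figure.

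**4. Effect of one carried success that is a death: 100/n points**

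| Group | n, all in FAS | Shift | n, 80% in FAS | Shift |
|---|---|---|---|---|
| CPA, MK-5592 | 50 | 2.0 | 40 | 2.5 |
| CPA, voriconazole | 25 | 4.0 | 20 | 5.0 |
| IA, MK-5592 | 10 | 10.0 | 8 | 12.5 |
| IA, voriconazole | 5 | 20.0 | 4 | 25.0 |

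**5. Illustration in CPA at the plan's 60% rate**

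Here k is the number of counted successes who were dead by Day 84. Intervals are Clopper-Pearson 95%.

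| k | MK-5592 | Voriconazole |
|---|---|---|
| 0 | 30/50 = 60.0% (45.2 to 73.6) | 15/25 = 60.0% (38.7 to 78.9) |
| 1 | 29/50 = 58.0% (43.2 to 71.8) | 14/25 = 56.0% (34.9 to 75.6) |
| 2 | 28/50 = 56.0% (41.3 to 70.0) | 13/25 = 52.0% (31.3 to 72.2) |

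The interval widths at k = 0 are 73.6 − 45.2 = 28.4 and 78.9 − 38.7 = 40.2 points. The documents give no death rate, so k cannot be estimated.

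**The case against.** The strongest reply is that the gap is mostly closed in practice. Overall response is mandatory at the EOT or discontinuation visit. If a dying patient is rated there and the clinical or radiological component cannot be judged, Tables 10 and 11 lead only to unable to determine or progressive disease, both failures. The CAC rates the endpoint, and Section 7.3.1 refers to an Adjudication Charter for endpoint definitions; the Charter was not supplied and Section 8.2.5.1.3 is redacted, so a death rule may exist in either. Patients not expected to survive the study are excluded. Efficacy is a secondary objective with no hypothesis. Scoring all-cause death as failure is also a convention rather than something these documents dictate: the notes to Table 1 use it for two prophylaxis studies, while the success definition given there for the treatment study does not mention death.

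Most of this stands, and it limits the size of the problem. It does not remove it. No visible text requires a rating at death, so a blank EOT rating remains possible, and no rating at discontinuation can account for a death that follows an EOT already rated a success. The exclusion criterion makes such deaths fewer but does not score them. Because efficacy is descriptive, the per-arm rates and intervals are the whole efficacy result, which is a reason to define a responder without ambiguity. The IA shifts are large only because the assumed groups are very small, and the primary IA route is uncommon.

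**Conclusion.** The concern holds on the visible text and should be fixed. Read literally, the rule can report a patient who died before the target day as a responder in FAS and ITT, chiefly in CPA at Day 84. The error is upward, at 2 or 4 points per death in CPA with groups of 50 and 25, and its total is unknown and may be zero. It is small against the interval widths and affects no test, sample size or stated precision figure. The conclusion rests on the assumed group sizes and full FAS entry, and on there being no death rule in the Charter or the redacted section, which could not be checked.

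**What to change.** In Section 8.2.5.1.4 and Tables 24 and 26, state that a known death from any cause on or before the target day (Day 42 for IA, Day 84 for CPA) is a failure in FAS and ITT, and that no response is carried past death. Apply the same principle, at the relevant day, to the secondary rates imputed in the same way, and check the wording against the Adjudication Charter. Keep carry-forward for other missing values, including early completion for cure, and report by arm how many values were carried forward and why.

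While editing, reconcile a separate conflict: the text excludes missing responses from the per-protocol analysis, whereas Table 26 lists carry-forward for it.

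The cost is a few sentences, a check against the Charter and one count by arm, with no added visits or data. Response rates may come out slightly lower. A limit remains: serious adverse events are routinely reported only to 14 days after treatment, so later deaths may be unknown for CPA patients who stop before Day 84 − 14 = 70 and IA patients who stop before Day 42 − 14 = 28. Some of those could still be carried forward as successes.

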**Table 1 Correlation Between Efficacy (Treatment or Prophylaxis for Invasive Fungal Infection) and Mean Exposure (Cavg)**

	P00041 (Aspergillosis)		P01899 (AML/MDS)		C/198-316 (GVHD)	
	Range of Cavg (ng/mL)	Response N(%)	Range of Cavg (ng/mL)	Response N (%)	Range of Cavg (ng/mL)	Response N (%)
MK-5592	55-277	24(4/17)	90-322	45.3(24/53)	22-557	55.6(35/63)
	290-544	53(9/17)	322-490	63.0(34/54)	557-915	79.4(50/63)
	550-861	53(9/17)	490-734	53.7(29/54)	915-1563	82.5(52/63)
	877-2010	71(11/16)	734-2200	72.2(39/54)	1563-3650	82.5(52/63)

P00041 study : Treatment of invasive fungal infection (IFI) as an endpoint. Success is defined complete response and partial response at the end of treatment using overall response  
P01899 study : Prophylaxis of IFI as an endpoint, AML/MDS subjects as a target population  
C/198-316 study : Prophylaxis of IFI as an endpoint, GVHD subjects as a target population  
P01899 and C/198-316 study: Failure is defined occurrence of a proven or probable IFI, use of empiric antifungal therapy treatment with a systemic antifungal other than study treatment for 5 days or more and death from all causes and/or premature discontinuation of study treatment. Success is defined other than failure.

[figure not shown]

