### 5.2.1.3 Treatment Duration

As a general rule, the treatment duration of all diseases is 84 days (77-84 days with considering the final treatment allowance). [However, for the subjects with zygomycosis, restart of the study therapy after finishing 84 day maximum treatment period or extension of treatment period could be done under the extension period with the prior approval from the Sponsor and obtaining the signing of a new informed consent from the only subject who have responded to the study therapy without intolerant toxicity if the investigator thinks that continuation of MK-5592 therapy would benefit the subjects with ample consideration of the MK-5592 profile and no alternative treatment in Japan (e.g. failure or intolerant to amphotericin B formulation). In addition to the above, in case of restart of the study therapy after the finishing 84 days, it can be done for the only subjects with same zygomycosis episode from the main study therapy (not new episode). The switch of the formulation (iv $\leftrightarrow$ tablet) could be done based on the subject's condition during the extension period but dose modification of MK-5592 must not be allowed. However, the study therapy must be discontinued when MK-5592 is marketed or the development of MK-5592 is discontinued in Japan. As a general rule, study medication information and adverse events are recorded (routine safety laboratory should be also monitored and recorded in the source document) during the study treatment over 84 days but refer to the specific procedure relating this matter including the details of information that should be recorded in CRF.] However, the treatment may be completed earlier if the subject does not need the therapy any longer by the investigator's discretion (e.g. cure of the target infection). The therapy may also be discontinued prematurely if the investigator decides that the patient is not capable of receiving further therapy (e.g. adverse event) although the investigator feels that the patient requires further treatment for the condition under study (refer to section 5.8 for discontinuation criteria).

In the event that the additional work-up does not result in a proven or probable IA diagnosis within 7 days of randomization, subjects should continue participation in the trial with possible IA.

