### **7.2.3 Immediate Reporting of Adverse Events to the Sponsor**

#### **7.2.3.1 Serious Adverse Events**

A serious adverse event is any adverse event occurring at any dose or during any use of Sponsor's product that:

- Results in death;
- Is life threatening;
- Results in persistent or significant disability/incapacity;
- Results in or prolongs an existing inpatient hospitalization;
- Is a congenital anomaly/birth defect;
- Is an other important medical event.

**Note:** In addition to the above criteria, adverse events meeting either of the below criteria, although not serious per ICH definition, are reportable to the Sponsor in the same timeframe as SAEs to meet certain local requirements. Therefore, these events are considered serious by the Sponsor for collection purposes.

- Is a cancer;
- Is associated with an overdose.

Refer to [Table 23](#) for additional details regarding each of the above criteria.

For the time period beginning when the consent form is signed until treatment allocation/randomization, any serious adverse event, or follow up to a serious adverse event, including death due to any cause, that occurs to any subject must be reported within 24 hours to the Sponsor if it causes the subject to be excluded from the trial, or is the result of a protocol-specified intervention, including but not limited to washout or discontinuation of usual therapy, diet, placebo treatment or a procedure.

For the time period beginning at treatment allocation/randomization through 14 days following cessation of treatment, any serious adverse event, or follow up to a serious adverse event, including death due to any cause, whether or not related to the Sponsor's product, must be reported within 24 hours to the Sponsor either by electronic media or paper. Electronic reporting procedures can be found in the EDC data entry guidelines. Paper reporting procedures can be found in the Investigator Trial File Binder (or equivalent).

Additionally, any serious adverse event, considered by an investigator who is a qualified physician to be related to the Sponsor's product that is brought to the attention of the

investigator at any time outside of the time period specified in the previous paragraph also must be reported immediately to the Sponsor.

All subjects with serious adverse events must be followed up for outcome.

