## **7.3 TRIAL GOVERNANCE AND OVERSIGHT**

### **7.3.1 Clinical Adjudication Committee**

A Clinical Adjudication Committee (CAC) will evaluate the following events for the purposes of confirming them according to the criteria in Section 8.0 – Statistical Analysis Plan.

- 1) Diagnosis of deep-seated fungal infection [For subjects with all queries closed, validity of deep-seated fungal infection diagnosed by investigators is assessed]
- 2) Overall Response [For subjects with all queries closed, validity of Overall Response assessed by investigator is assessed (Overall Response, Clinical Response, Radiological Response, Mycological Response)]

All personnel involved in the adjudication process will remain blinded to treatment allocation throughout the trial. Specific details regarding endpoint definitions can be found in the Adjudication Charter.

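### Section 8.2.5.1.4 does not say how death is scored, so as written a response success can be carried past a death to Day 42 (IA) or Day 84 (CPA)

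*Combined protocol and SAP*

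**What the plan says.** The primary efficacy endpoint is overall response as rated by the Clinical Adjudication Committee (CAC), at Day 42 for IA and Day 84 for CPA (8.2.3.1.1). Section 8.2.5.1.4 imputes a missing value by carry-forward in FAS and ITT, with this limit: "Baseline values will not be carried forward and if there is no data after treatment, the missing data will be considered as failure". It adds that a rating of unable to determine is also failure. No other outcome overrides carry-forward.

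Section 4.2.3 gives the categories: "Failure is defined as stable response, progressive disease and unable to determine". Neither Tables 10 to 12 nor Table 25 has an entry for death.

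Under 7.1.2.9, response "will be evaluated at Day 42, EOT(before the transition to the extension period) and switching formulation". Section 5.2.1.3 allows an early end of treatment (EOT): "the treatment may be completed earlier if the subject does not need the therapy any longer". A switch from IV to oral is allowed from Day 9 (5.2.1.1).

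Deaths are collected as serious adverse events from randomization to 14 days after treatment stops (7.2.3.1). The same section adds: "All subjects with serious adverse events must be followed up for outcome".

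**The concern.** A subject who has died by the assessment day had no response on that day. Counting that subject as a success can only raise the arm's rate. The path to this result runs through features that the protocol itself provides: early stopping after a good response, a required rating at formulation switch, and a required Day 42 rating in CPA, six weeks before the CPA endpoint. Deaths are foreseeable, since section 4.1.1 describes a generally poor prognosis for these infections.

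The other planned analyses of this endpoint would not correct it. In Table 26 the ITT and investigator-rated analyses also use carry-forward. The per-protocol analysis excludes subjects with missing post-treatment response (8.2.5.1.4), although Table 26 lists carry-forward for it too. None names death. What is at stake is the meaning of the reported rates, including the Day 42 IA rate, whose timing was chosen to allow a comparison with study 069 (4.2.3).

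**Working it through.** **1. Routes to a carried-forward success in a subject who has died.** These follow from 5.2.1.1, 5.2.1.3, 7.1.2.9 and 8.2.5.1.4. I assume that any rating made after treatment has started can be carried forward, since 8.2.5.1.4 excludes only baseline.

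- Success at an early EOT, then death before Day 42 (IA) or Day 84 (CPA).
- Success at a formulation switch, then death before the assessment day with no later rating.
- CPA only: favorable response at Day 42, then death before Day 84 with no later rating.

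In each case post-treatment data exist and the last rating is not unable to determine, so neither forced-failure rule applies.

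**2. Would the death be known?** Reporting runs to 14 days after the last dose. Status at the assessment day may therefore be unknown only when treatment stops before about Day 42 − 14 = 28 (IA) or Day 84 − 14 = 70 (CPA). Even then, a death is still captured if it is judged related to treatment or is the outcome of a serious event already being followed. Deaths on treatment, as in the second and third routes, are already in the database.

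**3. Planned numbers (8.2.7).** Cohort 2 has 90 subjects randomized 2:1, of whom 15 have IA. IA: 10 MK-5592 and 5 voriconazole. CPA: 90 − 15 = 75, so 50 and 25. I assume that all enter the FAS; a smaller FAS makes each case count for more.

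**4. Interval method, checked against the plan.** The Clopper-Pearson 95% limits for x successes in n are the 0.025 quantile of Beta(x, n − x + 1) and the 0.975 quantile of Beta(x + 1, n − x). The lower limit is 46.5% for 36/60 and 67.7% for 48/60, both as stated in 8.2.7.

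**5. Effect of one reclassified death.** The shift is 1/n: 1/50 = 2 points, 1/25 = 4, 1/10 = 10, 1/5 = 20. At the two planning rates in 8.2.7:

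| Group | n | Planning rate | As carried forward (95% CI) | One death scored as failure (95% CI) |
|---|---|---|---|---|
| CPA, MK-5592 | 50 | 60% | 30/50 = 60% (45.2–73.6) | 29/50 = 58% (43.2–71.8) |
| CPA, voriconazole | 25 | 60% | 15/25 = 60% (38.7–78.9) | 14/25 = 56% (34.9–75.6) |
| IA, MK-5592 | 10 | 60% | 6/10 = 60% (26.2–87.8) | 5/10 = 50% (18.7–81.3) |
| IA, voriconazole | 5 | 60% | 3/5 = 60% (14.7–94.7) | 2/5 = 40% (5.3–85.3) |
| CPA, MK-5592 | 50 | 80% | 40/50 = 80% (66.3–90.0) | 39/50 = 78% (64.0–88.5) |
| CPA, voriconazole | 25 | 80% | 20/25 = 80% (59.3–93.2) | 19/25 = 76% (54.9–90.6) |
| IA, MK-5592 | 10 | 80% | 8/10 = 80% (44.4–97.5) | 7/10 = 70% (34.8–93.3) |
| IA, voriconazole | 5 | 80% | 4/5 = 80% (28.4–99.5) | 3/5 = 60% (14.7–94.7) |

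In every row the new rate lies inside the interval before the change. The documents give no death rate or early-stop rate, so the number of cases cannot be estimated.

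**The case against.** **The charter and the committee.** The endpoint is a CAC rating, and 7.3.1 states: "Specific details regarding endpoint definitions can be found in the Adjudication Charter". That charter is not among the documents, and 8.2.5.1.3 is redacted. The CAC could also rate a subject who died as progressive disease or unable to determine, either of which is failure. This stands as a limit on certainty. A reader might infer that the trial will score deaths as successes; the documents do not show that. They show that the written imputation rule gives that result when nothing else intervenes, and nothing in the text requires the CAC to intervene.

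**Precedent.** The Table 1 footnote shows that two earlier prophylaxis studies counted as failure "death from all causes and/or premature discontinuation of study treatment". A reader might infer that the sponsor's established practice, or its intent here, is to count death as failure. The documents do not support that. Those studies had a different endpoint, and the same footnote describes the treatment study P00041, which is closer to this trial, as using overall response at the end of treatment with no death rule shown. The precedent is mixed.

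**Few cases, little weight.** Exclusion criterion 5 removes subjects not expected to survive the study. Early cure is less natural in CPA, where 4.2.3 says imaging findings rarely resolve. The primary objective is safety, and section 8.2.5 says "formal hypothesis testing for efficacy endpoints will not be conducted". All of this stands and keeps the point small. The 10- and 20-point IA shifts reflect group sizes of 10 and 5; any one reclassified subject would produce them.

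**Choice of estimand.** An unrelated death after a documented cure could reasonably be handled differently. It could, but then the plan should say so. Response at EOT is already a secondary endpoint (8.2.3.1.2) and records the state at stopping, so the Day 42/84 endpoint need not do that as well.

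**Conclusion.** The point holds as a gap in a stated rule. Section 8.2.5.1.4 specifies carry-forward and its exceptions, and death is not among them, so a success followed by death before the assessment day stays a success unless the CAC or its charter provides otherwise. Any resulting error raises the rate. Its size is about 2/4 points per case in CPA and 10/20 points per case in IA (MK-5592/voriconazole), if cohort 2 fills as planned and all subjects enter the FAS. The number of cases is unknown and may be zero. No error rate is affected and the sample size does not change. Carrying forward an EOT response in a living subject is defensible and is not questioned here. The correction is worth making because this is the named primary efficacy endpoint and the change costs almost nothing.

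**What to change.** Add one sentence to 8.2.5.1.4: in FAS and ITT, death from any cause on or before the assessment day (Day 42 for IA, Day 84 for CPA) counts as failure and overrides carry-forward. Apply it with the deaths already reported as serious adverse events. If the Adjudication Charter already contains such a rule, state it in 8.2.5.1.4 or refer to it there. The cost is one sentence and possibly slightly lower response rates.

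An optional extra is a vital-status check at Day 42 (IA) or Day 84 (CPA) for subjects who stopped early and have not withdrawn consent. It would find deaths after the 14-day window that are neither judged related nor the outcome of a serious event under follow-up. This is new data collection: it affects the flow chart and site procedures and may need consent wording and ethics review. The sentence in 8.2.5.1.4 is useful without it.
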